## 5.8 Patient Population

The patient population is composed of patients with joint surface lesions of the knee.

## 5.9 Indication for Use

The Agili-C™ scaffold is indicated for the treatment of an ICRS grade III or above knee-joint surface lesion(s), with a total treatable area of 1-7cm^2 and without severe osteoarthritis (Kellgren-Lawrence grade 0-3).

## 5.10 Number of Subjects

Up to 251 subjects, who were enrolled into the Pivotal study and are continuing follow up.

## 5.11 Number of Centers, Randomization and Allocation

Number of Centers participating: 22.

The subjects in the study will be randomized by site using variable block sizes.

The subjects in the study will stratified by extent of osteoarthritis, defined dichotomously by the Kellgren-Lawrence grade:

- Strata I: 0 & 1
- Strata II: 2 & 3

The study will recruit subjects in US and OUS sites.

## 5.12 Treatment Groups

- Experimental: Agili-C™
- Control: Surgical Standard of Care (SSOC)

## 5.13 Inclusion Criteria

1. 21 – 75 years

	
A Post Approval Multicenter Open-label Randomized Controlled Trial of Agili-C™ vs. Surgical Standard of Care (SSOC) for the Treatment of Joint Surface Lesions of the Knee
	
CLN0021-US Rev. 8 March 29, 2022

---	---	---

2. Up to 3 treatable, joint surface lesion(s), ICRS Grade IIIa or above, on the femoral condyles or trochlea
3. Symptomatic total treatable area 1-7 cm^2. Asymptomatic lesions will not be included in the calculation
4. Must be physically and mentally willing and able to comply with the post-operative rehabilitation protocol and scheduled clinical and radiographic visits
5. Signed and dated the IRB/Ethics Committee approved Informed Consent Form and HIPPA if applicable
6. Non-responsive to physical therapy for at least 3-4 weeks

#### **5.14 Exclusion Criteria**

1. KOOS Pain Subscale score at baseline is less than 20 or more than 65 (scale: maximum pain =0, pain free =100)
2. Bony defect depth deeper than 8mm, according to baseline MRI/X-ray/arthroscopy
3. Articular cartilage lesions in the tibia or the patella, ICRS grade IVa or above
4. Osteoarthritis of the index knee graded 4 according to the Kellgren-Lawrence Grading
5. Significant instability of the index knee according to IKDC Knee Examination Form 2000, Grade C (abnormal) or D (severely abnormal)
6. Malalignment more than 8 degrees varus OR 8 degrees valgus according to standing X-ray
7. Lack of functional remaining meniscus, at least 5mm rim at the end of the procedure
8. Meniscal transplantation in the past 6 months
9. Any known tumor of the index knee
10. Any known history of intra-articular or osseous infection of the index knee
11. Any evidence of active infection anywhere in the body. Urinary Tract Infection (UTI) patients can be included following antibiotic treatment, and provided that two consecutive cultures are negative (taken within at least 2 weeks of each other)
12. Any known history of inflammatory arthropathy or crystal-deposition arthropathy

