## A Post Approval Multicenter Open-label

## Randomized Controlled Trial of Agili-C™ vs.

Surgical Standard of Care (SSOC) for the  
Treatment of Joint Surface Lesions of the Knee

CLN0021-US

Rev. 8

March 29, 2022

Methods:	
 
• Candidates will be evaluated by the investigator based on an MRI (NMT one year old), X-ray (AP and Lateral; NMT one year old), clinical history and physical examination
 
• Prior to Screening, the candidate will sign and date the ICF using the IRB/EC approved form in accordance with local regulations
 
• Following signing of the informed consent, subjects will undergo Initial Screening using study questionnaires.
 
• The investigator will send the MRI and X-ray (AP and Lateral) for off-site evaluation. The X-ray will be evaluated by an independent radiologist, in order to determine the level of osteoarthritis according to Kellgren-Lawrence grade.
 
• In cases of K/L <4 and absence of clear exclusion criteria on MRI (as determined off-site), subjects will undergo Final Screening via Arthroscopy, not more than 90 days after Initial Screening. Arthroscopic findings will verify the subject's eligibility for study enrollment, and if found eligible will be Enrolled into the study and Randomized intra-operatively into either Agili-C™ or SSOC
 
• During the course of the procedure, mechanical-symptom generating lesions will be managed (such as synovectomy, loose body removal and partial meniscectomy) 
 
○ Agili-C™: Agili-C™ implantations will be performed via an arthrotomy or mini-arthrotomy procedure, using a designated surgical toolset
 
○ SSOC: microfracture and/or debridement procedures will be performed arthroscopically according to standard practice
 
 
 
• Ligamentoplasty is not allowed concomitantly
 

----------	--

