**A Post Approval Multicenter Open-label****Randomized Controlled Trial of Agili-C™ vs.**

**Surgical Standard of Care (SSOC) for the  
Treatment of Joint Surface Lesions of the Knee**

CLN0021-US

Rev. 8

March 29, 2022

13. Any known systemic cartilage and/or bone disorder, such as, but not limited to, osteoporosis, chondrodysplasia or osteogenesis imperfecta
14. BMI > 35
15. Chemotherapy in the past 12 months
16. Any previous surgical cartilage treatment (such as: microfracture, ACI, OATS, etc.) in the index knee within the last 6 months
17. Any previous ligamentous repair or malalignment correction in the index knee within the last 6 months
18. History of allergic reaction or intolerance of materials containing calcium carbonate or hyaluronate
19. Patient who is pregnant or intends to become pregnant during the study
20. History of any significant systemic disease, such as, but not limited to, HIV, hepatitis, HTLV, syphilis, and coagulopathies
21. Known substance or alcohol abuse
22. Participation in other clinical trials within 60 days prior to the study or concurrent with the study
23. Known insulin dependent diabetes mellitus
24. Unable to undergo either MRI or X-ray
25. Use of anticoagulation medication or antiaggregant medication; however up to 100 mg Acetylsalicylic acid (ASA) daily is allowed
26. Previous intra-articular steroid injection within the last 1 month
27. Prisoners
28. Uncontained lesion - Lack of vital bone wall, at least 2mm thick, completely surrounding the lesion - based on MRI/X-ray/arthroscopy
29. Inability to position the implant 2mm recessed relative to the articular surface - based on MRI/X-ray/arthroscopy

A Post Approval Multicenter Open-label

Randomized Controlled Trial of Agili-C™ vs.

Surgical Standard of Care (SSOC) for the  
Treatment of Joint Surface Lesions of the Knee

CLN0021-US

Rev. 8

March 29, 2022

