### **7.3.2 Final Screening/Procedure Visit (Visit 2)**

- Between 1 to 90 days after initial screening, subjects will undergo Final Screening (Visit 2) via arthroscopy. If found eligible, the subject will be enrolled into the study and randomized intra-operatively into either Agili-C™ or SSOC. Stratification will be performed based on K/L score performed off-site.
- For the SSOC group, lesion treatment will be determined according to subject's age, lesion size and K/L grade (Table 1) as per the control group selection algorithm (Figure 3).

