**Arthroscopy Procedure**

The arthroscopy procedure will be conducted according to hospital practice. Once subjects have fulfilled all the inclusion and none of the exclusion criteria, they will be enrolled into the study and randomized. The arthroscopy procedure should be video recorded according to hospital practice and documented post-procedure by the PI or study team on the relevant CRF assessment forms. The following structures should be carefully assessed by visualization and palpation:

- Synovia
- Patellar surface
- Trochlea surface
- Medial and lateral condylar surface

A Post Approval Multicenter Open-label

Randomized Controlled Trial of Agili-C™ vs.

Surgical Standard of Care (SSOC) for the  
Treatment of Joint Surface Lesions of the Knee

CLN0021-US

Rev. 8

March 29, 2022

- Medial and lateral tibial surface
- Medial and lateral meniscus
- Cruciate ligaments

Additionally, each lesion, regardless if symptomatic or not and if treated or not, should be documented according to the following parameters: location, severity (ICRS grade) and size (maximum length and maximum width). A company representative will be allowed to participate in the arthroscopy and to film the implantation procedure.

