### 10.2.2 Full Analysis Set

The full analysis set (FAS) will consist of all treated subjects in the Agili-C™ arm and treated subjects in the SSOC arm, for whom there is a valid overall KOOS score at baseline and at least one valid overall KOOS score post-baseline.

Consistent with ICH-E9, subjects with major entry violations will be excluded from FAS. “Major” is defined by having the potential to affect trial results and the decision of whether an entry violation is considered major will be performed by the Medical Director.

FAS will be used for the primary analysis.

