9.1 Analysis Populations

9.1.1 Full Analysis Set Population

The full analysis set (FAS) will consist of all treated subjects in the Agili-C™ arm and all treated subjects in the SSOC arm, for whom there is a valid overall KOOS score at baseline and at least one valid overall KOOS score post-baseline. A treated subject is defined as any subject who was randomized to any of the groups, and is not defined as a subject with major entry violation (as defined below).

In the FAS population, subjects who are treatment failures (as defined in Section 5.0) will have their 24-month KOOS score imputed as their baseline KOOS score. Thus, the treatment failure imputation will provide at least one valid overall KOOS score post-baseline and these subjects will be included in the primary analysis FAS population.

For all analyses performed on the FAS population, subjects will be analyzed according to the treatment arm to which they were randomized (regardless of the treatment actually received).

Consistent with ICH-E9, subjects with major entry violations will be excluded from FAS. Major entry violation is defined by having the potential to affect trial results and the decision of whether an entry violation is considered major will be performed by the Medical Director according to the following parameter - enrolment of subject with severe exclusion criteria, such as:

1. Bony defect depth deeper than 8mm
2. Uncontained lesion - lack of vital bone wall, at least 2mm thick, completely surrounding the lesion
3. Inability to position the implant 2mm recessed relative to the articular surface
4. Articular cartilage lesions in the tibia or the patella, ICRS grades IVa or above
5. Systemic cartilage and/or bone disorder

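### Subjects can be taken out of the primary analysis set after open-label, intra-operative randomisation, on evidence that may differ by arm, and no planned analysis puts them back

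*Protocol*

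**What the plan says.** **Order of events.** The trial is open-label (Protocol Section 2.0). At Visit 2 (Section 7.3.2), "If found eligible, the subject will be enrolled into the study and randomized intra-operatively into either Agili-C™ or SSOC". The arthroscopy text in the same section makes complete eligibility a condition: "Once subjects have fulfilled all the inclusion and none of the exclusion criteria, they will be enrolled into the study and randomized". Treatment comes after randomisation in the Visit 2 activity list.

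**Two exclusions in Section 5.14.** Exclusion 7 reads "Lack of functional remaining meniscus, at least 5mm rim at the end of the procedure". Exclusion 29 reads "Inability to position the implant 2mm recessed relative to the articular surface - based on MRI/X-ray/arthroscopy". The Synopsis says that during the procedure "mechanical-symptom generating lesions will be managed (such as synovectomy, loose body removal and partial meniscectomy"), without saying whether this comes before or after randomisation.

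**Removal from the primary set.** Section 10.2.2 excludes major entry violations from the FAS and uses the FAS for the primary analysis. Major means able to affect trial results, and "the decision of whether an entry violation is considered major will be performed by the Medical Director". Section 9.8.1 shows that this is the sponsor's own Medical Director. SAP Section 9.1.1 (the 24-month pivotal plan) ties the term to severe exclusion criteria and gives five examples, introduced as examples only. One is "Inability to position the implant 2mm recessed relative to the articular surface" and another is an uncontained lesion. The meniscal rim is not among them.

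**Agili-C only.** Section 10.4 scores failure to implant in an indicated subject as a treatment failure at baseline value. A contraindicated subject who is not implanted leaves the efficacy analyses.

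**Sensitivity analyses.** Section 10.10 has a worst-case analysis and a tipping-point analysis. Both vary missing values only.

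**The concern.** A primary set chosen after randomisation keeps the protection of randomisation only if a subject's chance of removal does not depend on arm. That is not secured here. The person who decides can know the allocation. Section 11.0 also schedules FAS effectiveness results for public posting after interim reports in October 2022, 2023 and 2024, so that person can see results before the final analysis. The test for major is influence on the results, and the list is open.

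Two of the SAP's five examples concern features that the implant procedure itself can expose. Section 5.15 recognises that the bone wall may be breached while the implantation site is made, and Appendix 5 sets the 2 mm recess only when the implant is pushed home. A control knee gets no such test.

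Neither document limits the decision to what was recorded before allocation. If difficult knees were removed more readily from one arm, the Month 60 comparison would be biased. The per-protocol set could not show it, because Section 10.3 makes it a subset of the FAS.

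**Working it through.** **1. Timing.**
- *Exclusion 29 and containment (exclusion 28):* as written, both rest on MRI, X-ray or arthroscopy, so they can be settled before randomisation. Nothing prevents a later re-judgement, and the occasion for one arises mainly in the Agili-C arm.
- *Exclusion 7:* it is dated to the end of the procedure, whereas the arthroscopy text requires every criterion to be settled before randomisation. If meniscal work can follow randomisation, both statements cannot be met. If it always precedes randomisation, the text should say so.

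**2. Reproducing the plan's power (Section 10.7.1).** Pooled t-test, one-sided 0.025, N = 120 and 59, SD 25. The standard error is 25 × √(1/120 + 1/59) = 3.98. For 13.9 points the noncentrality is 13.9/3.98 = 3.50 on 177 df, and power is 93.5%, as stated. The 80% power at 11.2 points also reproduces (80.0%).

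**3. How many subjects could be involved.** Up to 251 were enrolled (Section 5.10). The Month 24 FAS figures cover 160 + 79 = 239 (Section 10.7.1). The gap is 12, or 4.8%. It may include subjects with no usable KOOS score, so 12 is an upper bound on removals. A 2:1 split of 251 would be about 167 and 84, which puts about 7 Agili-C and 5 SSOC subjects outside the figures.

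**4. Effect on the difference.** Assumption: each restored subject has zero change, as under the protocol's rule for failures. New mean = old mean × N/(N + k). Starting means are those of the 13.9-point scenario.

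| Restored | Agili-C mean | SSOC mean | Difference |
|---|---|---|---|
| none | 34.4 | 20.5 | 13.9 |
| 12 Agili-C, N=160 | 34.4×160/172 = 32.0 | 20.5 | 11.5 |
| 12 Agili-C, N=120 | 34.4×120/132 = 31.3 | 20.5 | 10.8 |
| 7 Agili-C and 5 SSOC, N=160 and 79 | 34.4×160/167 = 33.0 | 20.5×79/84 = 19.3 | 13.7 |
| 12 SSOC, N=79 | 34.4 | 20.5×79/91 = 17.8 | 16.6 |

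In the third row the pooled SD rises to 25.6 and power falls from 93.5% to about 76%. If the Month 24 difference of 22.5 persisted, the same 12 would leave 43.0×160/172 − 20.5 = 19.5.

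**5. Effect on the error rate.** Suppose both arms truly improve by 20.5 points, and k zero-change subjects are removed from Agili-C only, leaving 120. The bias is 20.5 × k/120, which is 0.17 points for k=1 and 2.05 for k=12. The one-sided rejection rate becomes 2.8% and 7.4%, against a nominal 2.5%.

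**The case against.** A reader might infer that exclusions 7 and 29 can be settled only after randomisation, and that the rule therefore strips bad outcomes mainly from the device arm. The documents do not support that.

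- Exclusion 29 names pre-randomisation evidence.
- Exclusion 7 applies to both arms, since Section 6.2.3 allows partial meniscectomy in either. It is not among the SAP's examples, and no text says that a rim violation removes anyone from the FAS.
- Section 10.4 partly works against the device: an indicated Agili-C knee that cannot be implanted is scored as a failure, not dropped.
- No removals by arm are given. The rough split of 7 and 5 is about 4% of 167 and 6% of 84, which does not point to the device arm.

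There are also safeguards. The SAP analyses FAS subjects as randomised, its other three examples can be assessed in either arm, SAP Section 9.1.2 keeps violators in the safety set, and SAP Section 9.9 reports analysis-set counts by group. Finally, redefining the primary set now, with Month 24 results by arm already known, would itself be a post hoc change and would break comparability with the pivotal trial.

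All of this stands. It limits the claim about direction and size, and it argues against changing the primary FAS. It does not supply the missing blinding, deadline or evidence limit, and counts by group do not show what restoring the subjects would do to the estimate.

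**Conclusion.** The plan allows arm-dependent removal from the primary set and has no analysis that tests its effect. Whether such removal occurred, in which arm and in which direction, cannot be told from the documents.

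With zero change assumed for those restored, the 13.9-point scenario moves by about 0.2 points if the 12 split about 7 and 5. It falls to 11.5 or 10.8 if all 12 were Agili-C, and rises to 16.6 if all were SSOC. Only the all-Agili-C case at N=120 falls below the protocol's own 11.2-point mark for 80% power. A difference near the Month 24 value would survive every case shown. These are bounds resting on 251 being full enrolment, not estimates.

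This is an inexpensive gap to close, not evidence of bias. Separately, exclusion 7 and the pre-randomisation eligibility rule must be reconciled.

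**What to change.** 1. Keep the primary FAS as defined, for comparability with the pivotal trial.
2. Add to Section 10.10 one run of the primary model that restores, as randomised, every subject removed for a major entry violation or under the contraindicated clause of Section 10.4. State beforehand how a restored subject with no post-baseline score will be handled, with the same rule in both arms.
3. Freeze the removal list before Month 60 data are reviewed. Report it by arm, reason and date of the evidence.
4. Base any further removal only on evidence recorded before randomisation.
5. Reconcile exclusion 7 with the arthroscopy text in Section 7.3.2, and say where meniscal work falls relative to randomisation.

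The cost is a few sentences and one extra model run on data largely held already. The sensitivity result may show a slightly smaller effect. The primary result does not change.

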**A Post Approval Multicenter Open-label****Randomized Controlled Trial of Agili-C™ vs.**

**Surgical Standard of Care (SSOC) for the  
Treatment of Joint Surface Lesions of the Knee**

CLN0021-US

Rev. 8

March 29, 2022

13. Any known systemic cartilage and/or bone disorder, such as, but not limited to, osteoporosis, chondrodysplasia or osteogenesis imperfecta
14. BMI > 35
15. Chemotherapy in the past 12 months
16. Any previous surgical cartilage treatment (such as: microfracture, ACI, OATS, etc.) in the index knee within the last 6 months
17. Any previous ligamentous repair or malalignment correction in the index knee within the last 6 months
18. History of allergic reaction or intolerance of materials containing calcium carbonate or hyaluronate
19. Patient who is pregnant or intends to become pregnant during the study
20. History of any significant systemic disease, such as, but not limited to, HIV, hepatitis, HTLV, syphilis, and coagulopathies
21. Known substance or alcohol abuse
22. Participation in other clinical trials within 60 days prior to the study or concurrent with the study
23. Known insulin dependent diabetes mellitus
24. Unable to undergo either MRI or X-ray
25. Use of anticoagulation medication or antiaggregant medication; however up to 100 mg Acetylsalicylic acid (ASA) daily is allowed
26. Previous intra-articular steroid injection within the last 1 month
27. Prisoners
28. Uncontained lesion - Lack of vital bone wall, at least 2mm thick, completely surrounding the lesion - based on MRI/X-ray/arthroscopy
29. Inability to position the implant 2mm recessed relative to the articular surface - based on MRI/X-ray/arthroscopy

A Post Approval Multicenter Open-label

Randomized Controlled Trial of Agili-C™ vs.

Surgical Standard of Care (SSOC) for the  
Treatment of Joint Surface Lesions of the Knee

CLN0021-US

Rev. 8

March 29, 2022

## 5.15 Risks

The Agili-C™ implant is designed to treat joint surface lesions. The device is a biodegradable implant. The PI must be a qualified orthopaedic surgeon that has undergone pre-procedure training by the Sponsor. Following are risks that may occur while using the device:

- Improper implantation due to incorrect surgical technique and not according to the IFU.
- Creation of an improper implantation site may lead to implant breakage, instability, implant loosening and device failure.
- The defect site must exhibit vital bone on its entire circumference otherwise implant integration may not occur.
- Incorrect orientation of implant positioning may lead to improper healing.
- The implant must be inserted into the defect in a pressed fit manner. Non-press fit positioning may lead to failure due to lack of implant integration.
- Implantation using a non-designated surgical toolset may lead to implant fracture or misplacement.
- Incorrect use of the surgical toolset can lead to bone breakage, damage to neurovascular structures, bone cyst formation or improper implantation site creation. The surgeon must take into consideration the joint geometry especially with regard to notch, lateral and trochlear lesions. If there is a chance of bone wall violation during creation of the implantation site the implant should not be used.
- The device is composed of a porous brittle material, applying excess mechanical pressure during insertion may lead to implant breakage and particle generation. Particulate debris may cause an inflammatory response.
- If the implant is inserted at or above the articular cartilage, damage to the counter or adjacent tissue can occur, as well as particulate debris generation and synovitis.

**A Post Approval Multicenter Open-label****Randomized Controlled Trial of Agili-C™ vs.**

**Surgical Standard of Care (SSOC) for the  
Treatment of Joint Surface Lesions of the Knee**

CLN0021-US

Rev. 8

March 29, 2022

- Protruding edges, if left untreated, may lead to injury of nearby tissue. It is required that all implant sharp edges be removed, breakage of protruding edges may lead to fragment or particulate debris generation which may require removal.
- Idiosyncratic rejection reaction.
- Multiple implants may impinge, leading to implant fracture, bone fracture particulate debris and implant loosening and bone cysts may develop.
- Effusion, swelling, pain, synovitis, and systemic fever can occur due to infection, pseudo-septic reactions, reactive arthritis or aseptic arthritis.
- Inflammation might lead to degeneration of other articular surfaces, as well as ligament laxity and joint deformity. Large joint effusion might impact venous return and lead to leg edema. The neurovascular structures might be compromised.
- Suboptimal tissue ingrowth might occur: e.g. partial ingrowth, overgrowth, fibrous tissue ingrowth or partial coverage of the implant.
- Chronic pain reactions including complex regional pain syndrome might ensue.
- Implantation within avascular necrosis or cyst may lead to lack of implant integration and implant failure.
- Entrapment of soft tissue between the implant and the bone during implantation may lead to small gap followed by penetration of synovial fluid, lack of integration and cyst formation.
- Muscle atrophy.

These risks can be reduced significantly when the procedure is performed by a qualified orthopedic surgeon adhering to the IFU, trained in the use of the investigative device.

